11.7.2 Height and Weight (Treatment Cohort)

Height and weight will be measured with shoes off. Height and weight will be measured before the morning dose of the study drug during the Treatment Period. During the Treatment Period and at the Safety Follow-up Visit, height will be collected only for subjects ≤ 21 years of age (age on the date of informed consent/assent in the parent study).

11.7.3 Cystic Fibrosis Questionnaire-Revised (Treatment Cohort)

Subjects will be asked to complete the CFQ-R in their native language. The CFQ-R will be completed before the start of any other assessments, as noted in [Table 3-1](#).

- Subjects who are 12 and 13 years of age at Day 1 will complete the CFQ-R Child version themselves, and their parents/caregivers will complete the CFQ-R Parent version, on all visits, regardless of whether the subject subsequently turns 14 years of age during the study.
- Subjects who have turned 14 years of age during their participation in the parent study and have their Day 1 Visit for Study VX14-661-110 on the same day as the last parent study visit will complete the CFQ-R per the parent protocol requirement. At Day 15 and all subsequent visits, these subjects will complete the CFQ-R Adolescent/Adult version themselves.
- Subjects 14 years of age and older at Day 1 who do not have their Day 1 Visit for Study VX14-661-110 on the same day as the last parent study visit will complete the Adolescent/Adult version of the questionnaire themselves at all visits.

The questionnaires provide information about demographics; general quality of life, school, work, or daily activities; and symptom difficulties (pertaining to CF). Copies of the CFQ-R used in this study will be provided in the Study Reference Manual. Validated translations^{24,25} of the CFQ-R, if available, will be provided for participating centers in non-English-speaking countries.

11.7.5 Other Events Related to Outcome (Treatment Cohort)

11.7.5.1 Antibiotic Therapy for Sinopulmonary Sign/Symptoms (Treatment Cohort)

New or changed antibiotic therapy (IV, inhaled, or oral) for the following sinopulmonary signs/symptoms will be determined and documented at visits:

- Change in sputum
- New or increased hemoptysis
- Increased cough
- Increased dyspnea
- Malaise, fatigue, or lethargy

- Temperature above 38°C (equivalent to approximately 100.4°F)
- Anorexia or weight loss
- Sinus pain or tenderness
- Change in sinus discharge
- Change in physical examination (PE) of the chest
- Decrease in pulmonary function by 10%
- Radiographic changes indicative of pulmonary infection

For this study, a pulmonary exacerbation is defined as a change in antibiotic therapy (IV, inhaled, or oral) for any 4 or more of the above signs/symptoms. This definition is based on the definition of a pulmonary exacerbation used in the parent clinical studies including those investigating ivacaftor and VX-661/ivacaftor.^{35,36}

It is recommended that the study drug should not be interrupted during a pulmonary exacerbation unless, in the opinion of the investigator, it would be in the best interest of the subject.

The following information will be determined for protocol-defined pulmonary exacerbations:

- Number of pulmonary exacerbations
- Number of days with pulmonary exacerbations
- Time-to-first pulmonary exacerbation
- Number of pulmonary exacerbations requiring hospitalizations
- Number of days hospitalized for pulmonary exacerbations*
- Time-to-first hospitalization for pulmonary exacerbation
- Number of pulmonary exacerbations requiring IV antibiotic therapy
- Number of days on IV antibiotic therapy for pulmonary exacerbations
- Time-to-first IV antibiotic therapy for pulmonary exacerbations

*For each treatment group, the number of days hospitalized for pulmonary exacerbations will be analyzed as 48 weeks times the total numbers of days in hospital for pulmonary exacerbation, divided by the total number of weeks on treatment, for all subjects in the same treatment group.

11.7.5.2 Hospitalization for CF (Treatment Cohort)

At the visits indicated in [Table 3-1](#), subjects will be queried about planned and unplanned hospitalizations lasting ≥ 24 hours. The dates of hospitalizations and the reasons for hospitalizations will be documented.

For any hospitalization (unplanned and planned), the procedures for safety reporting should be followed (see [Section 13.1.2.3](#)).

The following information will be determined:

- Number of planned hospitalizations for CF (i.e., prophylactic antibiotic therapy)

- Number of all unplanned hospitalizations
- Number of days of all unplanned hospitalizations
- Time-to-first unplanned hospitalization

11.8 Safety

Safety evaluations will include AEs, clinical laboratory assessments, clinical evaluation of vital signs, ECGs, pulse oximetry, ophthalmologic examinations (subjects <18 years of age [age on the date of informed consent/assent in the parent study]), and PEs.

11.8.1 Adverse Events (Treatment Cohort)

All AEs will be assessed, documented, and reported in accordance with ICH GCP guidelines. [Section 13.1](#) outlines the definitions, collection periods, criteria, and procedures for documenting, grading, and reporting AEs. A separate document that details AE eCRF completion guidelines for investigators as well as training will be provided.

11.8.2 Clinical Laboratory Assessments (Treatment Cohort)

Blood and urine samples will be analyzed at a central laboratory. With the exception of Day 15 (when a lipid panel is not required), all blood samples will require a 4-hour fast before collection (at least a 4-hour fast is needed for the lipid panel). Fasting is not required at other time points unless specified in the assessment table. On Day 1/Returning Visit, blood samples will be collected before the first dose of the study drug. At all other scheduled visits, these samples will be collected at any time during the visit. Although blood samples are to be collected and analyzed at a central laboratory, a local laboratory may be used if a subject cannot return to the clinical study site for the mandatory liver function testing ([Section 11.8.6](#)). All urine pregnancy tests will be performed at the site.

Blood and urine samples for clinical laboratory assessments will be collected as shown in [Table 3-1](#). Laboratory test results that are abnormal and considered clinically significant will be reported as AEs (see [Section 13.1.1](#)).

Table 11-1 Safety Laboratory Test Panels

Serum Chemistry	Hematology	Urinalysis ^a
Glucose	Hemoglobin	Leukocyte esterase
Blood urea nitrogen	Erythrocytes	Nitrite
Creatinine	Mean corpuscular hemoglobin	Urobilinogen
Sodium	Mean corpuscular hemoglobin concentration	Urine protein
Potassium	Mean corpuscular volume	pH
Calcium	Reticulocytes	Urine blood
Chloride	Platelets	Specific gravity
Magnesium	Leukocytes	Urine ketones
Bicarbonate	Differential (absolute and percent):	Urine bilirubin
Inorganic phosphate	Eosinophils	Urine glucose
Total bilirubin, direct bilirubin	Basophils	
Alkaline phosphatase	Neutrophils	
Aspartate aminotransferase	Lymphocytes	
Alanine aminotransferase	Monocytes	
Lactate dehydrogenase	Coagulation Studies	
Gamma-glutamyl transpeptidase	Activated partial thromboplastin time	
Total protein	Prothrombin time	
Albumin	Prothrombin time International Normalized Ratio	
Creatine kinase		
Amylase		
Lipase		
Vitamin Levels		
Vitamins A, D, E, K, and B12		
Lipid Panel		
Total cholesterol, triglycerides		
Low-density lipoprotein (LDL)		
High-density lipoprotein (HDL)		

^a If urine is positive for leukocyte esterase, nitrite, protein, or blood, microscopic examination of urine will be performed for leukocytes, erythrocytes, crystals, bacteria, and casts.

The safety laboratory test panels are shown in [Table 11-1](#).

Pregnancy (β-human chorionic gonadotropin) testing for female subjects who are of childbearing potential from the time of the Day 1 Visit or at any point through the Safety Follow-up Visit (as defined in [Section 11.8.8.1](#)): Serum samples will be obtained as specified and analyzed at the central laboratory. Urine samples will be obtained as specified and all urine pregnancy tests will be performed at the site. **The urine pregnancy test on Day 1 (and the Returning Visit for subjects who re-enroll) must be negative before the first dose of study drug.**

Additional evaluations: Additional clinical laboratory evaluations will be performed at other times if judged to be clinically appropriate.

For purposes of study conduct, only laboratory tests done in the central laboratory may be used. At the discretion of the local investigator, local laboratories may be used for management of urgent medical issues. If a local laboratory test value is found to be abnormal and clinically significant, it should be verified by the central laboratory as soon as possible after the investigator becomes aware of the abnormal result. If it is not possible to send a timely specimen

to the central laboratory (e.g., the subject was hospitalized elsewhere), the investigator may base the assessment of an AE on the local laboratory value.

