3.1 Treatment Cohort

Table 3-1 Study VX14-661-110: Treatment Cohort

Event/Assessment ^a	Day -28 to Day -1	Treatment Period ^b						ETT Visit/ Departing Visit (Within 7 Days of Last Dose of Study Drug) ^{b,c,d,e}	Safety Follow-up Visit 28 (± 7) Days After Last Dose ^{c,d,e}
		Day 1 ^f / Returning Visit ^{b,g}	Day 15 (± 3 days)	Weeks 8, 16, 24, 36 (± 5 days)	Week 48 (± 5 days)	Weeks 60, 72, 84 (± 5 days)	Week 96 (± 5 days)		
Clinic visit		X	X	X	X	X	X	X	X

^a All assessments will be performed before dosing unless noted otherwise.

^b Selected visits may overlap with visits in the other qualified Vertex study: the Screening Visit of the other qualified Vertex study and a scheduled Treatment Period visit; the last required visit of the other qualified Vertex study and the Returning Visit; and the visit with the first dose of study drug in the other qualified Vertex study and the ETT Visit (refer to [Section 8.1.1.1](#) and [Section 8.1.1.3](#) for the timing/order of assessments in these cases).

^c If the subject prematurely discontinues study treatment, an ETT Visit should be scheduled as soon as possible after the subject decides to terminate study treatment ([Section 8.1.1.3](#)). Subjects who prematurely discontinue treatment will also be required to complete the Safety Follow-up Visit, approximately 28 (± 7) days after their last dose of study drug. If the ETT Visit occurs 3 weeks or later following the last dose of study drug, then the ETT Visit will replace the Safety Follow-up Visit, and a separate Safety Follow-up Visit will not be required.

^d If a subject is continuing onto commercially available VX-661/ivacaftor, the ETT Visit ([Section 8.1.1.3](#)) will be completed before dosing with commercial drug begins, and the Safety Follow-up Visit ([Section 8.1.1.2](#)) will not be required.

^e If a subject discontinues treatment to participate in another qualified Vertex study, the ETT Visit ([Section 8.1.1.3](#)) will be completed, and the Safety Follow-up Visit ([Section 8.1.1.2](#)) will not be required if the subject enrolls in the other study within 28 (± 7) days of the last dose of study drug in Study VX14-661-110.

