^p Symptom-targeted physical examinations will occur at any time during the study if triggered by AEs or if deemed necessary by the investigator (**Section 11.8.3**).

^q Pregnancy tests will be performed for all female subjects of childbearing potential. All urine pregnancy tests will be performed at the site.

Table 3-1 Study VX14-661-110: Treatment Cohort

Event/Assessment ^a	Day -28 to Day -1	Treatment Period ^b						ETT Visit/ Departing Visit (Within 7 Days of Last Dose of Study Drug) ^{b,c,d,e}	Safety Follow-up Visit 28 (± 7) Days After Last Dose ^{c,d,e}
		Day 1 ^f / Returning Visit ^{b,g}	Day 15 (± 3 days)	Weeks 8, 16, 24, 36 (± 5 days)	Week 48 (± 5 days)	Weeks 60, 72, 84 (± 5 days)	Week 96 (± 5 days)		
Standard 12-lead ECG ^f		X	X	Weeks 8, 16, 24	X	Week 72	X	X	X
Vital signs ^s		X	X	X	X	X	X	X	X
Pulse oximetry ^s		X	X	X	X	X	X	X	X
Spirometry ^t		X	X	X	X	X	X	X	X
Hematology ^u		X ^v	X	X	X	X	X	X	X
Coagulation ^u		X ^v		X	X	X	X	X	X
Serum chemistry ^u		X ^v	X	X	X	X	X	X	X
Lipid panel ^u		X ^v		X	X	X	X	X	X
Vitamin levels ^u		X ^v		X	X	X	X	X	X
Urinalysis		X		X	X	X	X	X	X
PK sampling				Week 24 ^w				X	
Other events related to outcome ^x		X	X	X	X	X	X	X	X
Meal(s) or snack(s) at site ^y		X	X	X	X	X			
Study drug count			X	X	X	X	X	X	

^f All standard 12-lead ECGs will be performed before dosing and after the subject has been supine for at least 5 minutes (Section 11.8.4). At the Day 1 and 15 Visits, ECGs will be collected before dosing and at 1.5 and 4 hours after the morning dose. A window of ± 15 minutes will be allowed around the nominal times for all postdose ECG assessments. ECGs collected on Day 1 before dosing will be performed in triplicate. If study drug is not administered on the day of the visit (i.e., because of study drug interruption), only 1 ECG will be collected.

^s Vital signs and pulse oximetry will be collected before dosing and after the subject has been at rest (seated or supine) for at least 5 minutes (Sections 11.8.3 and 11.8.5).

^t Spirometry must be performed for all subjects before dosing and should be performed pre-bronchodilator (Section 11.7.1).

^u With the exception of Day 15, all blood samples will require a 4-hour fast before collection.

^v Blood samples will be collected before the first dose of study drug.

^w A single blood sample for PK will be collected within 60 minutes before dosing (Section 11.5.1).

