^x Other events related to outcome include assessments relating to pulmonary exacerbations, administration of antibiotic therapy for sinopulmonary signs or symptoms, and hospitalizations (Section 11.7.5).

^y Fat-containing food such as a standard CF high-fat, high-calorie meal or snack will be provided at the site to subjects after all predose assessments have occurred.

Table 3-1 Study VX14-661-110: Treatment Cohort

Event/Assessment ^a	Day -28 to Day -1	Treatment Period ^b						ETT Visit/ Departing Visit (Within 7 Days of Last Dose of Study Drug) ^{b,c,d,e}	Safety Follow-up Visit 28 (± 7) Days After Last Dose ^{c,d,e}
		Day 1 ^f / Returning Visit ^{b,g}	Day 15 (± 3 days)	Weeks 8, 16, 24, 36 (± 5 days)	Week 48 (± 5 days)	Weeks 60, 72, 84 (± 5 days)	Week 96 (± 5 days)		
Study drug dosing ^z		Day 1 to Week 96							
Concomitant medications		Continuous from signing of the ICF and Assent (where applicable) through the Safety Follow-up Visit							
Concomitant treatments and procedures		Continuous from signing of the ICF and Assent (where applicable) through the Safety Follow-up Visit							
AEs and SAEs ^{bb}		Continuous from signing of the ICF and Assent (where applicable) through the Safety Follow-up Visit							
AE: adverse event; CF: cystic fibrosis; CFQ-R: CF Questionnaire–Revised; ECG: electrocardiogram; ETT: Early Treatment Termination; ICF: informed consent form; PK: pharmacokinetic; SAE: serious adverse event; ██████████									

^z The study drug should be administered every 12 hours (± 2 hours) within 30 minutes of starting a meal with fat-containing food such as a standard CF high-fat, high-calorie meal or snack (Section 10.2). On days of scheduled visits, the morning dose of study drug will be administered at the site after predose assessments have been completed. The final dose of study drug will be administered the evening before the Week 96 Visit. If the Returning Visit coincides with the last Visit of the other Vertex study, the morning dose of VX-661/ivacaftor may be supplied by the other Vertex study.

^{bb} SAEs that occur after the Safety Follow-Up Visit and are considered related to study drug(s) will be reported to Vertex GPS within 24 hours as described in Section 13.1.2.2.

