9 STATISTICAL ANALYSIS

9.1 General Considerations

Continuous variables will be summarized using the following descriptive summary statistics: the number of subjects (n), mean, standard deviation (SD), median, minimum value (min), and maximum value (max).

Categorical variables will be summarized using counts and percentages.

Visit Windowing Rules: [Section 11.1](#) defines the windows for protocol-defined visits. Note, spirometry assessments, BMI, weight, and height will be used for both efficacy and safety purposes. Their measurements will follow the visit windowing rules for efficacy parameters.

The windows will be applied for both scheduled and unscheduled visits. If no measurement is available within a visit window, the assessment will be considered missing for the visit. If there is more than one measurement available within the same visit window, the following rules will be used:

For all safety parameters, if there are multiple measurements within a visit window, then

- The record closest to the target day will be used, with the exception of the threshold analysis in which the worst record will be used.
- If there are multiple records within the same distance of the target day, the latest record will be used.
- The SFU visit will not be windowed; instead, the nominal visit will be used in relevant analyses.

For all efficacy parameters, if there are multiple measurements within a visit window, the record at the scheduled visit will be used. Otherwise,

- If there are multiple records with the same distance to the target day, the latest record will be used.
- If there are no measurements at the scheduled visit, then the record closest to the target day will be used.

- Assessments at the Early Treatment Termination (ETT) Visit will follow the windowing rules for regular visits.
- Assessments at SFU Visit will follow the windowing rules for regular visits if they fall within the upper boundary of the window for the last scheduled visit. If assessments occur after the upper boundary of the window for the last scheduled visit, they will be still considered as the SFU Visit.

Incomplete/Missing data will not be imputed, unless otherwise specified.

Outliers: No formal statistical analyses will be performed to detect or remedy the presence of statistical outliers, unless otherwise specified.

Unscheduled **Visits:** Unscheduled visit measurements will be included in the following:

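### Day 15 glucose is drawn without a required fast, yet it counts fully in the worst-record hyperglycemia summary for the whole treatment-emergent period

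*Protocol*

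**What the plan says.** **Fasting.** Footnote u of Protocol Table 3-1, attached to hematology, coagulation, chemistry, lipids and vitamins, reads: "With the exception of Day 15, all blood samples will require a 4-hour fast before collection". Protocol 11.8.2 gives the same rule with a reason: "With the exception of Day 15 (when a lipid panel is not required), all blood samples will require a 4-hour fast before collection". The exemption therefore rests on lipids not being collected on Day 15. Serum chemistry is collected that day, and Table 11-1 lists glucose in that panel.

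**Timing.** Footnote a sets the default: "All assessments will be performed before dosing unless noted otherwise". Section 11.8.2 then fixes one visit, "On Day 1/Returning Visit, blood samples will be collected before the first dose of the study drug", and frees the rest: "At all other scheduled visits, these samples will be collected at any time during the visit".

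**Food.** Table 3-1 marks a site meal on Day 1, Day 15 and Weeks 8 to 84, and none at Week 96, ETT or Safety Follow-up. Footnote y says that a fat-containing "meal or snack will be provided at the site to subjects after all predose assessments have occurred".

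**Analysis.** SAP 9.7.2 summarizes laboratory values and changes by visit, shifts by visit, and the number and percentage of subjects meeting a threshold criterion over the entire 110 TE Period. SAP 9.1 uses the record closest to the target day, "with the exception of the threshold analysis in which the worst record will be used". SAP Table 11-3 starts the hyperglycemia bands at values above ULN up to 8.9 mmol/L. Neither 9.1 nor 9.7.2 mentions fasting status.

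**The concern.** Serum chemistry is a named part of the primary safety endpoint. A worst-record count over a whole period assumes that the records are comparable, because a single value decides each subject's category. Here one scheduled record per subject is taken under a different condition from all the others, and the difference pushes glucose in the direction that the hyperglycemia bands are meant to detect. All subjects receive the same drug, so no concurrent untreated group would show the same Day 15 excess. A reader of the study report would see a percentage of subjects above ULN on treatment and could not tell how much of it depends on one non-fasting draw.

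**Working it through.** No figure in the plan needs to be reproduced. The check is a count of visits, a reading of the threshold rule, and a statement of scale.

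**1. How many glucose visits are non-fasting?** Chemistry in Table 3-1 is due post-baseline at Day 15 (1), Weeks 8, 16, 24, 36 (4), Week 48 (1), Weeks 60, 72, 84 (3) and Week 96 (1): 1 + 4 + 1 + 3 + 1 = 10 scheduled treatment visits. ETT and Safety Follow-up come on top and are under the fasting rule. A non-fasting draw is permitted at 1 of the 10. The sentence "Fasting is not required at other time points unless specified in the assessment table" adds no further scheduled visit, because footnote u specifies the fast for the others.

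**2. Can a Day 15 sample follow the site meal without a deviation?** Yes. The fast does not apply, the any-time sentence displaces the predose default of footnote a, and the meal is marked for that day. Table 3-1 also schedules Day 15 ECGs at 1.5 and 4 hours after the morning dose, and the dose is taken within 30 minutes of starting the meal. The subject is therefore normally at the site for about 4 hours after eating.

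**3. What does the threshold rule do with that value?** For subject *i*, let *g* be the Day 15 glucose and *m* the highest of all other records in the period. The worst record is max(*g*, *m*), which is never below *m*. So for any cut-off *c*:

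- count above *c* with Day 15 = (subjects with *m* > *c*) + D(*c*)
- D(*c*) = number of subjects with *g* > *c* and *m* ≤ *c*, which is zero or more.

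Including Day 15 can only raise the count above a cut-off. D(*c*) is not itself the size of the food effect: an early, genuine rise in glucose would also fall in it. It is the number of subjects whose classification depends on the non-fasting value alone, which is what a reader needs to see.

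**4. Scale.** SAP 6.2 gives 1,044 enrolled subjects. If all were dosed and sampled, each percentage point of subjects in D(*c*) is 0.01 × 1,044 = 10.4 subjects. The documents give no glucose distribution, so the percentage cannot be stated.

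**5. The any-time wording at other visits.** Post-baseline lipid panels are due at Weeks 8, 16, 24, 36, 48, 60, 72, 84 and 96, which is 9 scheduled treatment visits. A site meal is marked at the first 8. At those 8 the fast still applies, but the any-time sentence takes the draw out of the predose group that footnote y places ahead of the meal.

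**The case against.** **The exemption is deliberate and Day 15 is already visible.** SAP Table 11-1 maps Day 15 to its own analysis visit, and values, changes and shifts are reported by visit. This stands for the by-visit tables, where a label is enough. It does not help the whole-period threshold count, which has no visit dimension.

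**Removing Day 15 would discard safety data.** This also stands, and it is why both counts should be shown. A true early glucose effect must not disappear from the report.

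**Study 106 results, including placebo, are presented alongside (SAP 7.4).** That is not a concurrent control. These documents do not give Study 106's fasting rules or visit schedule, so it cannot be assumed to carry the same Day 15 artefact.

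**A stronger reading of 11.8.2.** A reader might infer that the any-time sentence lets sites take fed lipid samples throughout the study. The documents do not support this. The fast is stated in the same paragraph and repeated in footnote u, so the two rules apply together: any time in the visit, provided the subject has fasted. A fed lipid sample at Weeks 8 to 84 would be a protocol deviation. Section 11.1 also points to an earlier draw, since it places blood sampling after spirometry, which must be done before dosing. What remains is wording that a site could misread.

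**Conclusion.** The concern holds for Day 15 glucose in the whole-period hyperglycemia count. It needs no site error: following the protocol and SAP as written produces a worst-record summary that mixes one non-fasting value with values from visits where a fast is required. The direction is upward, and the lowest band (above ULN up to 8.9 mmol/L) is the most exposed. The size is unknown. The only premise from outside the documents is the general one that glucose tends to be higher after food.

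The any-time sentence in 11.8.2 is a secondary matter of wording.

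Two further inferences should not be drawn. First, a uniform fasting baseline cannot be assumed, and so neither can a clean fasting-to-fed shift. The SAP safety baseline is the last value before first active treatment in the parent study or Study 110, whichever is earlier, and the parent studies' fasting rules are not given. Even at Study 110 Day 1, footnote f of Table 3-1 lets active sites rely on same-day parent-study assessments, while Protocol 8.1.1.1 says that these may have to be repeated. Second, the documents give no size for a post-meal rise in triglycerides, so no estimate of subjects crossing the lipid thresholds is supported.

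**What to change.** **SAP 9.7.2 and 11.3.** Present the hyperglycemia threshold count twice: with all records, as now, and without the Day 15 draw. Define the omitted record by its nominal visit, because the Day 15 analysis window runs from study day 2 to 36 and can also take in unscheduled samples. Label the Day 15 glucose change and shift as non-fasting in the by-visit tables. The cost is one extra row or table and a footnote; no sample, visit or safety record is lost.

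**Protocol 11.8.2 (wording only).** Reconcile the any-time sentence with footnotes a, u and y. One way is to state that, except at Day 15, samples are drawn after the 4-hour fast and, where a meal is served at the site, before that meal. This form also fits Week 96, ETT and Safety Follow-up, where no site meal is marked. The cost is one sentence. Spirometry already has to precede dosing, so the visit needs no new step.
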